2.4.2. Effect-modifier analyses of primary outcome. Changing effects during follow up

In the main analyses, observation time will be censored at 183 days after enrolment. However, the effect of OPV may vary over the 6 months and by season.

Furthermore, the risk of COVID-19 may also vary during the 6 months of follow-up: During 2020 and 2021, Guinea-Bissau experienced three waves of COVID-19 infections, during which the risk of COVID-19 has been elevated (figure). Based on this, we have identified periods of higher transmission: Before 1 October 2020, 1 January - 1 April 2021 and after 1 July 2021.

Finally, health staff have been on strikes during a large part of 2021. We will assess whether effects differ by periods of observation.

[figure not shown]

Figure: Number of confirmed COVID-19 cases per week in the Bissau sector (source www.ACCOVID.com).

Time varying effects will be investigated in the models described below.

Table 6. Potential effect modifiers of the primary outcome – changing effects during observation period

Population	Per-protocol population
Observation period	From: enrolment To: 183 days after enrolment Censoring: None
Potential effect modifiers	a) First 3 vs subsequent 3 months of follow up b) Season of follow-up (Rainy: June-November, Dry: December-May) c) Periods of intense transmission (Figure) d) Periods with health staff on strike
Failure definition	Death or first post-enrolment admission for infection or consultation for infection.
Statistical tools	Cox-proportional hazards model with interaction term, adjusted for the zone (stratification variable in the randomisation), age and box1 factors. Robust standard error to adjust for same-house clustering.
Outline stata code For analysis:	<pre>stset outcome, f(combinedoutcome=1) origin(dateenrol) enter(dateenrol) exit(dateenrol+183) id(studyidnumber)</pre> 
a) Time since enrolment:
 <pre>g splitdate1=dateenrol+91 if dateenrol+_t >splitdate1 stsplitt time, at(0) after(splitdate1) replace time=time+1 recode time . =0</pre> <pre>stcox group#time time b11.zone b50.agegroup b1.box1var1 b1.box1var2 ..., vce(cl house)</pre> 
Where EfM is the potential effect modifier (categorical variable) and [box1var1] [box1var2] etc. are the background factors from Box1 which affect the [group]-estimate for the main outcome by more than 10%
 
b) Splitting the observation time 1 December 2020 and 1 June 2021 to define rainy season (before 1 December and after 1 June) and dry season

	
(December-May) This variable “rain” (0/1) will be included as an effect modifier.
 
stcox group#rain rain b11.zone b50.agegroup b1.box1var1 b1.box1var2 ..., vce(cl house)
 
Where EfM is the potential effect modifier (categorical variable) and [box1var1] [box1var2] etc. are the background factors from Box1 which affect the [group]-estimate for the main outcome by more than 10%
 
c) Splitting the observation time at 1 October 2020, 1 January, 1 April 2021 and 1 July 2021 to define exposed time intervals: Before 1 October 2020, 1 January-1 April 2021 and after 1 July 2021. This variable “expos” (0/1) will be included as an effect modifier.
 
stcox group#expos expos b11.zone b50.agegroup b1.box1var1 b1.box1var2 ..., vce(cl house)
 
Where EfM is the potential effect modifier (categorical variable) and [box1var1] [box1var2] etc. are the background factors from Box1 which affect the [group]-estimate for the main outcome by more than 10%
 
d) Splitting the observation time into periods affected and not affected by strikes among health staff.
 
stcox group#strike stike b11.zone b50.agegroup b1.box1var1 b1.box1var2 ..., vce(cl house)
 
Where EfM is the potential effect modifier (categorical variable) and [box1var1] [box1var2] etc. are the background factors from Box1 which affect the [group]-estimate for the main outcome by more than 10%

--	---

2.5 Additional analyses of secondary outcomes.

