#### **Outcomes:**

**Primary outcome:** Composite outcome of the first of death, hospitalisation for infection and/or consultation for infection at the health centre

**Secondary outcomes:** Episodes with self-reported infectious disease morbidity. Episodes with self-reported infectious disease morbidity suspected to be caused by COVID (three or more of the following: fever, cough, sore throat, extreme fatigue, loss of smell/taste). Either of the components of the composite outcome described above included repeated events.

**Statistical analysis:** Data will be analysed in Cox proportional hazards models, with time since randomization as the underlying time, to provide hazard ratios (HRs) with 95% CIs for comparison of the intervention and control groups. With the exception of the primary outcome, data will be analysed as a multiple failure time data set. Age in groups of 5 years and suburb will be adjusted for. Clustering within houses will be adjusted for.

**Sample size:** The Bandim Health Project has purchased 1700 doses of OPV. The trial will include participants until the 1700 doses have been used. With a samples size of 3400, half getting OPV, the trial can show a reduction in the combined risk of mortality (which has been around 2% in this age group in our study area) and severe morbidity after 6 months of follow-up from a total of 10% to 7.2% (i.e. a 28%

reduction) with 80% power and alpha of 0.05. Since only individuals above the age of 50 years are eligible to enter the trial, only few houses will have several participants and we expect a very limited effect of clustering.

**Explanation to participants:** Participants will be given thorough information about Coronavirus, about precautions to be taken, and about the study (Appendix 2).

**Timeline:** A Gantt diagram is presented in Figure 1.

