1.6 Statistical analyses

1.6.1 Statistical model

The outcome rates will be compared by randomisation arm in Cox proportional hazards models, with time since randomization as the underlying time, to provide hazard ratios (HRs) with 95% CIs. The main results will be adjusted for age (in 5-year age-bands) and zone (based on which the randomisation was stratified). Clustering within houses will be adjusted for. With the exception of the primary outcome, data will be analysed as a multiple failure time data set. All statistical tests will be 2-tailed and $p \leq 0.05$ considered statistically significant.

Prior to implementing the trial, stories of experimental COVID-19 vaccines planned to be tested in Africa had been circulating on social media, and many perceived the OPV, which we were providing in the present trial, as one of these experimental vaccines. We have therefore encountered high refusal rates, especially in the intervention arm. As this may have resulted in baseline imbalances, we will present both the 'crude' result (only adjusted for age and zone) and adjusted results where we will adjust for background factors which affect the estimated effect of OPV on the primary outcome by more than 10%. The background factors to be investigated are presented in Box 1.

In subsequent analyses of the trial dataset, we intend to use targeted maximum likelihood estimation (TMLE) (section 2.6.2). These analyses will be reported later.

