2.2 Primary analysis of primary outcome

The rates of the primary outcome (a composite outcome of the first of death, hospitalisation for infection and/or consultation for infection at the health centre) within 6 months after enrolment will be compared in Cox proportional hazards models with time since enrolment as the underlying timescale.

The primary analysis of the primary outcome is described in more detail in table 1.

Table 1: Primary analysis of primary outcome

Population	Per-protocol population
Observation period	From: enrolment To: 183 days after enrolment Censoring: None
Failure definition	Death or first post-enrolment admission for infection and/or consultation for infection registered at a health centre.
Statistical tools	Cox-proportional hazards model, adjusted for the zone (stratification variable in the randomisation) and age. Robust standard error to adjust for same-house clustering.
Outline stata code	<pre>stset outdate, f(combinedoutcome=1) origin(dateenrol) enter(dateenrol) exit(dateenrol+183) stcox group b11.zone b50.agegroup b1.box1var1 b1.box1var2 ..., vce(cl house) Where [box1var1] [box1var2] etc. are the background factors from Box1 which affect the [group]-estimate by at least 10% Check of proportional hazards assumption¹: estat phtest, detail stphplot, adj(zone agegroup box1var box2var) strata(group)² stcox group, strata(zone agegroup box1var box2var) vce(cl house) /// tvc(group) tezp(_t)</pre>

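### The primary Cox model has no calendar-time term, so it gives no protection against health-staff strikes if the two arms entered at different dates

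*SAP*

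**What the plan says.** SAP 2.2, Table 1, specifies a "Cox-proportional hazards model, adjusted for the zone (stratification variable in the randomisation) and age". Box 1 factors are added only if they move the estimate by at least 10%. The clock starts at enrolment and stops at 183 days. Box 1 (SAP 2.1) contains no enrolment date, season, wave or strike variable, and the TMLE covariates in SAP 2.6.2 contain none either.

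SAP 2.4.2 defines three periods of higher COVID-19 transmission and adds: "Finally, health staff have been on strikes during a large part of 2021. We will assess whether effects differ by periods of observation". Calendar time is used only for effect modification: season of enrolment in Table 5, and season of follow-up, transmission period and strike period in Table 6.

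On how people entered, SAP 1.2 randomises houses within zone. SAP 1.6.1 says: "We have therefore encountered high refusal rates, especially in the intervention arm". The protocol's sample-size paragraph says: "The trial will include participants until the 1700 doses have been used". Neither document has a rule that keeps entry dates in the two arms aligned.

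**The concern.** On a time-since-enrolment clock, people who entered months apart share a risk set. This is harmless if entry dates have the same distribution in both arms. If they do not, a change in the event rate over calendar time is read as a vaccine effect. Strikes are the obvious source of such a change, because one primary component is a consultation recorded at a health centre.

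Randomisation balances the houses, but entry happens when a person is visited and agrees. Allocation influenced agreement, so date of entry is a post-randomisation quantity. The SAP already accepts that refusal may have unbalanced the arms and offers covariate adjustment for it. Calendar time, which it separately identifies as affecting risk, is not among the candidates. At stake is the single hazard ratio on which the trial will be judged.

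**Working it through.** **1. The plan's design figure.** Inputs from the protocol: "With a samples size of 3400, half getting OPV"; 10% versus 7.2% at 6 months (a 28% reduction); "with 80% power and alpha of 0.05". Tests are two-sided (SAP 1.6.1). Schoenfeld with HR 0.72: 4 × (1.960 + 0.842)² / (ln 0.72)² = 291 events needed. Expected: 1700 × (0.10 + 0.072) = 292.4, power 80.2%. The figure reproduces, and HR 0.72 serves below as a yardstick.

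**2. COVID-19 waves, on the SAP's own dates.** High transmission: before 1 October 2020, 1 January to 1 April 2021, after 1 July 2021. Share of 183 days spent in a high period, by entry date:
- 1 July 2020: 92/183 = 50.3%
- 1 August 2020: (61 + 30)/183 = 49.7%
- 1 October 2020: 90/183 = 49.2%
- 1 January 2021: (90 + 2)/183 = 50.3%

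Every entry day from 1 July 2020 to 1 April 2021 gives 49.2-50.3%. The share departs from one half only outside that window: 66.7% at 1 June 2020 and 1 May 2021, 83.6% at 1 June 2021. The large-sample Cox HR under no vaccine effect, with a 2-4-fold wave rate and 40% or 30% of OPV participants (against 50% of controls) entering in the early half, is 1.000-1.002. With entry from 1 June 2020 to 1 June 2021 it is 1.003-1.010.

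**3. Strikes.** The documents give neither dates nor an effect on event rates, so these inputs are assumptions: entry uniform within each half of 1 August 2020 to 1 April 2021 (midpoint 1 December 2020); strikes start between 1 January and 1 May 2021 and last to the end of follow-up; the rate of the composite is k = 2 to 4 times higher before the strike; 50% of controls enter in the early half, against 40% (10 points) or 30% (20 points) of OPV participants.

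Let p be the mean share of follow-up before the strike, r = 1 + (k − 1)p, and s the OPV early share. Then null ratio = [s·r(early) + (1 − s)·r(late)] / [0.5·r(early) + 0.5·r(late)].
- Strike from 1 January, k = 4: p = 0.505 early, 0.022 late; r = 2.515 and 1.066; denominator 1.7905. s = 0.4: 1.6456/1.7905 = 0.92. s = 0.3: 1.5007/1.7905 = 0.84.
- Strike from 1 May, k = 2: p = 0.978 and 0.495; r = 1.978 and 1.495; denominator 1.7365. s = 0.4: 1.6882/1.7365 = 0.97. s = 0.3: 1.6399/1.7365 = 0.94.

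The corresponding large-sample Cox calculation over monthly strike starts gives 0.92-0.97 and 0.84-0.95. Reversing the imbalance gives about 1.03-1.08 and 1.06-1.17.

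Sensitivity to the assumed dates: entry from 1 July 2020 lowers the extremes to 0.91 and 0.825. Strikes ending on 1 July 2021 shrink the lower limits to 0.95 and 0.90.

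**4. Effect of stratifying.** In a simulation with no vaccine effect (1700 per arm, risk near 10%, one drop in the rate, ratio 2 or 3, 150 trials per setting), the unadjusted Cox model gave:
- no imbalance: HR about 1.00, about 5% rejection;
- 10 points: HR 0.93-0.95, about 9% rejection;
- 20 points: HR 0.85-0.91, 13-27% rejection.

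Stratified by month of enrolment, HR was 0.99-1.01 and rejection 3-6%. Simulation error on the rejection rates is about 2 to 4 points.

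**The case against.** The strongest reply is that the needed imbalance is undocumented. A reader might infer that the arms were enrolled at different times. The documents do not say so: the rumours are dated before the trial and linked to refusal, not to timing. A refusal difference that stays constant changes who and how many enter, not when. A reader might also infer that waves and strikes changed the primary event rate sharply. The SAP says COVID-19 risk was elevated and that strikes occurred, but gives no effect on the primary outcome. It does not say whether the two study health centres closed. All of this stands, and so does the finding that waves contribute almost nothing for most plausible entry dates.

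The composite is also only partly exposed. Deaths come mainly from the HDSS and admissions from telephone calls. On the protocol's planning figures (about 2 points of mortality within a 10% total), a twofold fall with deaths unchanged needs the other 8 points to fall to 3, and a fourfold fall needs them to drop to 0.5. The fourfold end is therefore demanding. Strikes and the 2021 waves may also overlap and partly offset.

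Two existing safeguards help but do not close the gap. Zone adjustment absorbs calendar differences between zones, not differences between arms within a zone. The Table 6 season, wave and strike models include the period main effect, so they do adjust for it. But they take one factor at a time, are supplementary, and return period-specific effects rather than one overall hazard ratio.

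**Conclusion.** The point holds as a conditional risk. The primary model has no calendar-time protection, and balance of entry dates is not assured. It is not a demonstrated bias, and with matched dates it is exactly zero. COVID-19 waves are not a material route for entry between July 2020 and 1 April 2021; strikes are the main one.

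On the assumptions above, a 10-point imbalance would shift a null hazard ratio to about 0.92-0.97, and a 20-point imbalance to 0.84-0.95, in either direction according to the sign of the imbalance. On the log scale, against the design value of 0.72, this is roughly a tenth to a quarter of the target effect (ln 0.97/ln 0.72 = 0.09; ln 0.92/ln 0.72 = 0.25) and a sixth to a half (0.16 and 0.53). The 10-point shift is under 10%, so the SAP's change-in-estimate rule could miss it even if enrolment date were a candidate. The sample size and stated power are unaffected. This is a cheap improvement worth making, not a fault that invalidates the primary analysis.

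**What to change.** 1. Add month of enrolment by arm to Box 1 as a descriptive row. This alone shows whether the concern is live.
2. In Table 1, stratify the primary Cox model by month of enrolment or by calendar period, outside the 10% rule. Month of enrolment is the simpler choice: add `strata(enrolmonth)` to the existing `stcox` line. Within a stratum, equal follow-up days then fall within about a month of each other on the calendar. Calendar-period stratification needs an `id()` in `stset` and a split of follow-up, as Table 6 already does for the wave dates.
3. If the sponsor prefers to leave Table 1 unchanged, prespecify the stratified model as a named sensitivity analysis that reports one overall hazard ratio beside the primary one.
4. State the strike start and end dates, which Table 6(d) also needs.

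Cost: SAP wording, a few lines of Stata and a little more analysis work, with a negligible loss of precision. No new data are needed beyond the strike dates, since each participant's enrolment date is already held.

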2.5.1. Effect-modifier analyses of secondary outcomes

Analogous to effect modifications analyses for the primary outcomes (Tables 5 and 6), we will assess whether the same potential effect modifiers are effect modifiers of the secondary outcomes (Tables 2-4).

2.6. Further sensitivity analyses

2.6.1 Narrower outcome definitions

In sensitivity analyses we will explore if the conclusions are robust to:

Narrower definitions of the planned outcomes:

- Suspected infectious deaths rather than all cause deaths
- Severe infections with reported loss of weight
- Infections with reported COVID-19 diagnoses, tests performed and positive tests

2.6.2 Alternative analytical approaches

Due to the potential imbalance which may have resulted due to the differential refusal rates, we will in subsequent analyses use targeted maximum likelihood estimation^{2,3} (TMLE) in a re-analysis of primary and secondary outcomes. The modelling step will include the categorical variables sex, visual weight-classification (1-10), chronic illness, symptoms on the day of enrolment, medicine intake in the past month, ethnic group, whether signed or fingerprinted the consent form, and the continuous variable, age.

Specification of the models used will be guided by a machine learning algorithm (Super Learner)⁴ using both a default library of prediction models as well as a more elaborate library.

3. References

2. van der Laan MJ, Rubin D. Targeted Maximum Likelihood Learning. *The International Journal of Biostatistics* 2006; **2**(1).
3. van der Laan MJ, Rose S. Targeted Learning: Causal Inference for Observational and Experimental Data Berlin: Springer.
4. Polley EC, van der Laan MJ. Super Learner In Prediction. U.C. Berkeley Division of Biostatistics: Working Paper 266., 2010.
